As secondary endpoints, this study will evaluate patient reported outcomes through 12 months follow up. Comparisons of patient-reported outcomes such as pain in patients undergoing palliative radiotherapy are notoriously difficult. These can be impacted by the initial indication for palliative radiation (i.e. oligoprogression versus uncontrolled symptom), presence or absence of other tumors outside the target(s), subsequent therapies after treatment, and co-morbidities. This study will attempt to reduce this heterogeneity by studying the secondary endpoints within pre-specified subgroups. Additionally, this study will evaluate PROs using the reliable change index, which allows evaluation of the change of individual patient PROs of comparison to their own baseline.

The RCI utilizes the known retest reliability and standard deviation of a test to calculate the standard error of measurement and standard error of the difference between scores [Jacobson, 1992]. This value represents the level of change associated with statistically significant change from baseline. RCI is calculated as follows:

$$RCI = \frac{x_2 - x_1}{S_{diff}}$$

Where  $x_2 - x_1$  represents an individual's change between timepoints. This can also be reported as a difference in population mean.  $S_{diff}$ , the standard error of the difference between the two scores accounting for reliability of the test, is calculated as:

$$S_{diff} = \sqrt{2(S_E)^2}$$

$$S_E = s_1 \sqrt{1 - r_{xx}}$$

Where  $S_E$  is the standard error of measurement of the test,  $s_1$  is the standard deviation of the test results at the initial time point, and  $r_{xx}$  is the test-retest reliability of the measure. The test-retest reliabilities of PROMIS domains used in this study have been previously evaluated in patients with musculoskeletal conditions and range from 0.85-0.92 [Deyo, 2016].

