The RCI will be calculated for each individual patient for pain score, PRO-CTCAE, and each PROMIS domain between baseline and the 3, 6, and 12 month time points. In order for a change to be deemed statistically reliable at a 90% confidence interval, the Z-score of the RCI must be greater than 1.645. The 90% confidence interval is standard use in the literature when calculating RCI because it increases the sensitivity in detecting reliable change and defines a change which occurs in only 5% of healthy individuals in either direction [Stein, Gray, Schmitt, Hensel]. Changes that exceed this threshold in either direction are likely due to actual change rather than due to chance. Individual changes are reported as either significant increase, significant decrease, or no change.

Mean RCI for each time-point and domain will be calculated to determine significant change on a population level for each sub-group. The  $S_{diff}$  for each domain will be used to calculate a minimum important change at each time-point based on a 90% confidence interval. Lastly, the proportion of individuals in each histology cohort group whose RCI indicated significant increase, significant decrease, or no change in PRO scores will be reported.

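### Sub-group mean RCI is to show significant change, but the plan gives no standard error or limit for a mean, and S_diff with 1.645 does not supply a 90% test

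*Combined protocol and SAP*

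**What the plan says.** Section 11.2 (Study Endpoints) defines the RCI as a change score divided by S_diff. Here S_diff = √(2·S_E²) and S_E = s₁·√(1 − r), with s₁ the baseline SD and r the test-retest reliability. For the PROMIS domains the reliabilities were "previously evaluated in patients with musculoskeletal conditions and range from 0.85-0.92". No reliability is given for the pain score or PRO-CTCAE, to which the RCI is also applied. It is computed for each patient "between baseline and the 3, 6, and 12 month time points". For a change to count as reliable, "the Z-score of the RCI must be greater than 1.645", and the reason given is that this limit "defines a change which occurs in only 5% of healthy individuals in either direction".

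The same section then moves from patients to groups. It says of the change in the numerator: "This can also be reported as a difference in population mean". It continues: "Mean RCI for each time-point and domain will be calculated to determine significant change on a population level for each sub-group". It adds that S_diff "for each domain will be used to calculate a minimum important change at each time-point based on a 90% confidence interval". Section 11.3 says only that the RCI serves for the before-and-after QoL comparison. Neither section gives a standard error, confidence interval, degrees of freedom or cut-off for a mean.

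**The concern.** A claim of significant change in a group needs the sampling error of a mean. That error depends on how many patients contribute and on how much their changes differ. S_diff reflects neither: it is the noise in one person's difference score when nothing has truly changed. The 1.645 limit is sound for that person, but its justification does not extend to an average.

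Patient-reported outcomes are secondary objectives, and Sections 1.6.2 and 11.2 plan to read them within four sub-groups, each of which may have as few as 10 enrolled patients. If the individual limit is used for means, a real average improvement or worsening may be reported as no significant change. With very few patients, noise may be reported as change. If it is not used, there is no group rule at all, and the analyst would choose one after seeing the data.

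**Working it through.** **Inputs from the documents.** r = 0.85 to 0.92 (Section 11.2, PROMIS only); cut-off 1.645; at least 10 patients in each of four cohorts (Protocol Summary); 67 enrolled, so 67/4 ≈ 17 for an even split.

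**Assumptions.** The SD of change is not given; the main illustration sets it equal to the baseline SD s₁, with a range of 0.7 to 1.2 s₁ as sensitivity. PRO attrition is not given either. Borrowing the 30% loss planned for local control at 6 months takes 10 and 17 to about 7 and 12; n = 5 is added for 12 months. The half-SD effect is illustrative.

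**1. The plan's own figure.** For one patient with measurement error only, the RCI is standard normal. P(Z > 1.645) = 0.050 per side, 0.100 in total, so the individual limit reproduces.

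**2. The bar if carried over to a mean.** S_diff = √2 · s₁ · √(1 − r) = 0.548 s₁ (r = 0.85) or 0.400 s₁ (r = 0.92). Multiplied by 1.645 this is 0.901 s₁ or 0.658 s₁. Neither contains n.

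**3. Error and detection of that bar.** With SD of change = s₁, the mean change has standard error s₁/√n.
- Two-sided error = 2·P(Z > bar·√n), with the bar in units of s₁. Example, n = 10 and r = 0.85: 2·P(Z > 0.901 × 3.162) = 0.0044.
- Detection of a true 0.5 s₁ change = P(Z > (bar − 0.5)·√n). Same example: P(Z > 1.268) = 0.102.
- Comparator: paired t test, 5% per side, with limit t(0.95, n − 1)/√n.

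| n | 90% t limit (in s₁) | Error, r = 0.85 | Error, r = 0.92 | Detection, r = 0.85 | Detection, r = 0.92 | Detection, paired t |
|---|---|---|---|---|---|---|
| 5 | 0.95 | 4.4% | 14.1% | – | – | – |
| 7 | 0.73 | 1.7% | 8.2% | 14% | 34% | 32% |
| 10 | 0.58 | 0.44% | 3.7% | 10% | 31% | 43% |
| 12 | 0.52 | 0.18% | 2.3% | 8% | 29% | 49% |
| 17 | 0.42 | 0.02% | 0.67% | 5% | 26% | 63% |

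At n = 10 to 17 the bar is 1.14 to 2.13 times the t limit (0.658/0.580 and 0.901/0.423). The t limit allows for estimating the SD, so at n = 5 or 7 it can exceed the bar even where the bar's error is below 10%.

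**4. Sensitivity to the SD of change.** From 0.7 to 1.2 s₁, the error runs from under 0.001% to 8% at n = 10 to 17, and from 0.07% to 15% at n = 7. If baseline and follow-up were uncorrelated (SD of change √2 · s₁), it would be 14.1% at n = 10 with r = 0.92.

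**5. Why dividing by √n alone fails.** Using 1.645/√n as the limit for mean RCI assumes that patients differ only by measurement error. With SD of change = s₁ the error is 2·P(Z > 1.645 × S_diff/s₁) = 2·P(Z > 0.901) = 37% or 2·P(Z > 0.658) = 51%, whatever n is. The plan itself expects changes to vary with "presence or absence of other tumors outside the target(s), subsequent therapies after treatment, and co-morbidities".

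**The case against.** A reader might infer that the plan tests mean RCI against 1.645. It never says so. The limit is introduced and justified for individuals, and the S_diff-based minimum important change can be read as a benchmark of size. What is established without any assumption is that the group rule is missing; the error rates describe one way of filling the gap. That stands, and the figures are conditional on it. Against it, the wording about population-level significance and about a difference in means makes the carry-over the natural reading.

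A reader might also infer that the carried-over test is always far too strict. The documents do not support that. RCI is planned at 12 months, Section 11.4 expects short survival, and at n = 5 with r = 0.92 the illustrative error is already 14%.

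The inputs are also limited. The 30% loss concerns imaging at 6 months, while questionnaires may be completed by phone or online, so PRO loss could differ. Ten per cohort is a floor and 17 only an even split: with three cohorts at 10, the fourth could reach 67 − 30 = 37. These points weaken any single figure. They do not restore a 10% error rate.

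Finally, the RCI was chosen mainly to judge individual change, and that use is valid.

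**Conclusion.** The concern holds in conditional form. The plan announces a population-level significance finding for each sub-group without a standard error or limit for a mean, and the quantities it does supply cannot serve as one. If they are used, the bar stays at 0.66 to 0.90 baseline SD for any n, and the nominal 10% is not met in general. At about 10 or more patients the test is usually too strict; with fewer, its direction depends on the unknown SD of change and the number with data.

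Confidence is high for the omission and for the fixed bar, which follow from the text and the stated reliabilities. The error and detection figures rest on the assumed SD of change and attrition, and cover PROMIS only.

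It would be wrong to infer that the trial's main conclusions are at risk. The co-primary endpoints, sample size, toxicity monitoring, individual RCI classification and the cohort proportions increased, decreased or unchanged are unaffected. This should be corrected, but it is a secondary-endpoint matter.

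**What to change.** Amend Section 11.2 as follows.

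- Keep 1.645 × S_diff for classifying individual patients and for the cohort proportions.
- For each sub-group, domain and time point, report the mean change from baseline (or mean RCI) with a 90% t interval, using the observed SD of the changes divided by √n. Give n, and say that the result applies to patients with data at that time point.
- Do not use 1.645/√n as the limit for mean RCI.
- If 1.645 × S_diff is displayed beside means, state that it is a benchmark of size and not a significance test.
- Label the intervals descriptive and unadjusted for multiplicity. With the five PROMIS measures of Section 5.6 there are at least 4 × 3 × 5 = 60, of which about 60 × 0.10 = 6 would exclude zero by chance if nothing changed. Pain and PRO-CTCAE add more.

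The cost is a few sentences and trivial programming, with no new data and no change in sample size.

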### **1.6.2 Scientific Rationale for Study Design**

Tumor burden incurs significant morbidity in terms of symptomatology, including pain, dyspnea, hemoptysis, and mass effect on surrounding organs. Palliative hypofractionated radiotherapy is known to be a useful modality for control and/or amelioration of such symptoms. However, large tumors are difficult to treat with traditional palliative methods. Hypofractionated radiotherapy may offer insufficient control and SBRT may be associated with a high rate of toxicity.

Dose escalation using SFRT may offer improved local control, symptom relief, and reduced toxicity compared with traditional radiotherapy methods. Also, SFRT has been associated with significant activation of systemic anti-tumor cytokines and chemokines.

Our initial pilot study of SBRT has been successful thus far, demonstrating that Lattice SBRT is safe and effective treatment for large tumors. However, the pilot study has thus far demonstrated significant heterogeneity in the patient population. Patients are enrolled for different indications and tumor types have varied (i.e. treatment of oligoprogressive disease, palliation of pain, palliation of lung cancer for dyspnea, palliation of sarcoma for bleeding). Further, Lattice SBRT has been followed with varied treatments (i.e. medical therapies, surgery), and sometimes no treatment. Given this heterogeneity, objectively determining the effect of Lattice SBRT both on tumor control and patient QoL is difficult.

This trial of Lattice SBRT will attempt to define efficacy and safety using dual primary endpoints for all patients: local tumor control at 6 months and rate of treatment related grade 3+ CTCAE v5.0 toxicity. Secondary endpoints will then evaluate patient reported QoL in 4 pre-specified sub-groups: sarcomas, thoracic malignancies, gastrointestinal malignancies, and pelvic cancers.

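### Section 11.2 plans population-level significance statements in roughly 48 to 84 patient-reported outcome cells, using a threshold calibrated to one patient's change and no multiplicity rule or exploratory label, so the error rate is undefined.

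*Combined protocol and SAP*

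**What the plan says.** Section 11.2 computes a reliable change index (RCI) for each patient, covering "pain score, PRO-CTCAE, and each PROMIS domain between baseline and the 3, 6, and 12 month time points". The index is the patient's change divided by S_diff, the standard error of one person's difference, which is built from the baseline standard deviation and the test-retest reliability. The decision limit is: "In order for a change to be deemed statistically reliable at a 90% confidence interval, the Z-score of the RCI must be greater than 1.645". Its stated justification is that this "defines a change which occurs in only 5% of healthy individuals in either direction".

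The next paragraph moves to the group level: "Mean RCI for each time-point and domain will be calculated to determine significant change on a population level for each sub-group". It adds that S_diff "will be used to calculate a minimum important change at each time-point based on a 90% confidence interval". It gives no separate group-level test, standard error or significance level.

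The sub-groups are set in Section 1.6.2: "Secondary endpoints will then evaluate patient reported QoL in 4 pre-specified sub-groups: sarcomas, thoracic malignancies, gastrointestinal malignancies, and pelvic cancers". Section 11.2 gives the reason: "This study will attempt to reduce this heterogeneity by studying the secondary endpoints within pre-specified subgroups".

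The Protocol Summary, Section 2.0 and Section 11.2 all class the patient-reported outcomes as secondary. The exploratory label is attached only to the blood markers. In Section 11.3, descriptive statistics are assigned to demographic and clinical characteristics, including toxicity, while the RCI is to be used to compare quality of life before and after treatment.

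**The concern.** Two gaps combine. First, the plan intends to declare significance in every domain, time point and sub-group cell, but does not say which cell decides, in what order cells are read, or how error is shared among them. Fixing the sub-groups in advance settles which cells exist, not which one carries the conclusion. Second, the criterion for a group mean is missing. The 1.645 limit belongs to one patient's score, and a mean over n patients has a different sampling distribution.

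Cohorts may have as few as 10 patients, and fewer will remain at later visits. A reader of the results could not tell a real cohort-level change from a chance one, and could not know how often chance ones should be expected. The quality-of-life headline could also be chosen after the data are seen. The primary endpoints are not affected.

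**Working it through.** **Inputs from the documents**
- Time points: 3 (3, 6 and 12 months, Section 11.2).
- Sub-groups: 4 (Section 1.6.2).
- PROMIS domains: 4 in the Protocol Summary; 5 in Sections 2.0, 5.4 and 5.6, which add Pain Interference.
- Cohort size: at least 10 (Protocol Summary); average 67/4, about 17.
- Loss: up to 30% not evaluable for local control at 6 months (Section 11.2). Applying this to patient-reported outcomes is an assumption; it takes 10 to 7.
- Test-retest reliability r: 0.85 to 0.92 (Section 11.2).

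**The plan's own figure.** The two-sided 10% normal limit is 1.6449, with 0.0500 in each tail. The stated 1.645 reproduces, for an individual.

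**Number of cells**
- PROMIS only: 4 × 3 × 4 = 48, or 5 × 3 × 4 = 60.
- Five domains plus pain score and PRO-CTCAE as one score each: 7 × 3 × 4 = 84.

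**Reading A: each cell is a valid two-sided 10% test and there is no true change.** Expected false claims are 0.10 × cells: 4.8, 6.0 and 8.4. Sub-groups contain different patients, so they combine as 1 − (1 − p)^4, where p is the chance of a false claim in one sub-group. Within a sub-group, p was simulated with equally correlated normal statistics (200,000 draws). The correlation is assumed.

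| Cells | Correlation 0 | 0.5 | 0.8 |
|---|---|---|---|
| 12 (one domain) | 0.72 | 0.66 | 0.56 |
| 60 | 0.998 | 0.97 | 0.82 |
| 84 | 0.9999 | 0.99 | 0.86 |

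For 48 independent cells, 1 − 0.9^48 = 0.994. With perfect correlation inside each sub-group, the floor is 1 − 0.9^4 = 0.34.

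**Reading B: the mean RCI is compared literally with 1.645.** Let k be the standard deviation of the individual RCIs. The mean then has standard error k/√n, and with no true mean change the per-cell error is

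P = 2 × [1 − Φ(1.645 × √n / k)].

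If patients differ only by measurement error, k = 1. Otherwise, with equal variances at both visits and baseline-to-follow-up correlation ρ, k = √[(1 − ρ)/(1 − r)]. The documents do not give ρ. At ρ = 0.5, k = √(0.5/0.15) = 1.83 for r = 0.85, and √(0.5/0.08) = 2.5 for r = 0.92. At ρ = 0.8, k = 1.15 and 1.58.

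Worked example, n = 10 and k = 2.5: 1.645 × 3.162 / 2.5 = 2.081, so P = 0.0375. Over 84 independent cells, 1 − (1 − 0.0375)^84 = 0.96.

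Chance of at least one false claim over 84 independent cells:

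| n per cohort | k = 1 | 1.5 | 1.83 | 2.0 | 2.5 |
|---|---|---|---|---|---|
| 7 | 0.001 | 0.27 | 0.77 | 0.92 | 0.999 |
| 10 | 0.00002 | 0.04 | 0.31 | 0.54 | 0.96 |
| 17 | <0.0001 | 0.0005 | 0.02 | 0.06 | 0.43 |

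The same written rule therefore has an error rate anywhere from near 0 to near 1. Correlation between cells would lower the larger figures.

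**The case against.** A reader might infer that the plan tests every group mean at 10%, so that at least one false claim is nearly certain. The documents do not support this. The 90% limit is introduced for individual patients and justified by how often healthy individuals exceed it. S_diff is the error of one person's difference and is never divided by √n. The group-level sentence sets no level of its own. The more literal reading compares the mean RCI with the individual limit. If patients vary only by measurement error, that rule almost never produces a false claim: 2 × 10⁻⁷ per cell at n = 10. Near-certainty under it needs small cohorts and widely dispersed change, and that dispersion is not in the documents.

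The cell count is also softer than one number suggests. The domain lists differ between sections. Section 2.0 ties the pain scale to patients with pain and PRO-CTCAE to those without, while Section 5.6 lists both without that split. Nothing specifies item-level PRO-CTCAE testing, so a higher count on that basis is not supported.

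Finally, the trial is single-arm and sized for precision, no patient-reported result drives a decision, and Section 11.2 itself warns that such comparisons are difficult.

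All of this stands against a claim of a specific inflated rate. It does not remove the gap. The plan says significance will be determined, with no error rate attached under either reading. The near-zero case needs patients' true scores to move together, yet Section 11.2 says later therapies, other tumors and co-morbidities affect these outcomes.

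**Conclusion.** The concern holds in this form: Section 11.2 commits to population-level significance statements in about 48 to 84 cells of secondary endpoints, without a key contrast, multiplicity control or exploratory label, and with a threshold that does not define a group-level test. The error rate is unknown rather than known to be high.

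Its size depends on the reading. With valid 10% tests and correlation from 0.8 down to 0, the chance of at least one false claim over 60 to 84 cells is about 82% to over 99.9%, with 6 to 8 expected. With the literal 1.645 rule, the chance over 84 independent cells is near 0 when only measurement error operates, or when cohorts of about 17 have high baseline-to-follow-up correlation. It reaches 0.96 at n = 10 and 0.999 at n = 7 when that correlation is 0.5 and reliability 0.92. The correlations, and carrying the 30% loss over to patient-reported outcomes, are assumptions.

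This should be corrected. It bears on how every sub-group quality-of-life result may be described, but not on the primary endpoints.

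**What to change.** In Section 11.2, replace the sentence "Mean RCI for each time-point and domain will be calculated to determine significant change on a population level for each sub-group" with:

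*Mean change and its 90% CI, computed from the observed SD of change and the number of patients assessed, will be presented for each domain, time point and sub-group. These results are exploratory, are not adjusted for multiplicity and will not be described as statistically significant.*

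Keep the 1.645 rule for classifying individual patients only, and say that the S_diff-based minimum change serves that same purpose. The planned proportions of patients with reliable increase, decrease or no change can stay.

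If a confirmatory patient-reported statement is wanted, name one contrast in advance and control it with a family-wise method. For example, one measure at one time point across the four sub-groups could use Holm's method at a two-sided 10% family-wise level, with everything else labelled exploratory.

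The cost is two or three sentences, with no new data or patients. The price is that sub-group results can no longer be called significant. Under the Holm option, the smallest of the four p-values would have to be below 0.10/4 = 0.025.

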### **11.3 Data Analysis**

Demographic and clinical characteristics including treatment toxicity will be summarized using descriptive statistics. RECIST 1.1 will be used to determine local control per the protocol described in Appendix E. The RCI will be used to compare the QoL scores between before and after treatment with Lattice SBRT.

### **11.4 Power Analysis and Sample Size**

Approximately 67 evaluable patients will be enrolled. The proposed sample size was chosen based on clinical considerations, to allow for establishment of an expected 6-month local control rate and treatment related grade 3+ CTCAE toxicity rate for treatment of very large tumors.

After discussing with internal and external stakeholders, we determined that a clinically reasonable bound on local control at 6 months would be 15%. Approximately 47 patients would be required to determine local control with a 95% confidence interval of +/- 15%. However, patients with large tumors needing Lattice SBRT are expected to have a short median survival. Based on our prior experience, we expect 20-30% of patients will complete Lattice SBRT but may be unevaluable for the primary endpoint. Enrolling 67 patients with an up to 30% drop out rate would ensure at least 47 evaluable patients to create our clinically acceptable 95% CI estimate for local control at 6 months.

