Study Population:	67 adult patients will be enrolled and treated, (with a goal of 47 evaluable patients), $\geq 18$ years of age with ECOG $\leq 2$ . At least 10 patients will be enrolled in each cohort (soft tissue sarcomas, thoracic cancers (including esophageal), abdominal, and pelvic cancers). All genders and races will be included. Any participants who do not receive treatment will be replaced.
Phase:	N/A
Description of Sites / Facilities Enrolling:	This is a single-institutional study conducted at Washington University School of Medicine
Description of Study Intervention:	5-fraction Lattice SBRT delivered to 20 Gy with a simultaneous integrated boost (SIB) to 66.7 Gy.
Study Duration:	16 months plus 2 weeks for treatment and 12 months follow up
Participant Duration:	2 weeks of treatment plus 12 months follow up.

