## **4.5 Strategies for Recruitment and Retention**

Our institution sees a high volume of patients that are referred for palliative radiotherapy.

The primary source of patients who are eligible for this study will be radiation oncologists within our department. The most likely service lines to see patients with large tumors in need of palliative radiotherapy are sarcoma, thorax (i.e. lung cancer), gastrointestinal, gynecologic (pelvic), and palliative. [name] (sarcoma, thorax, gastrointestinal) is the PI, and the other service line chiefs are enthusiastic about this trial and are listed as co-investigators: [name] (Thorax), [name] (Gastrointestinal), [name] (Gynecologic), [name] (Palliative). Additionally, a full-time research coordinator will be assigned to this study who will assist in screening patients who are referred to our department for palliative radiotherapy for a large tumor.

With the current rate of patients in need of palliative radiotherapy presenting to our department, we anticipate approximately 100 patients per year will be eligible for this protocol. A conservative estimate is that 50% of these patients will consent to participate in this study. This yields an estimated accrual of 50 patients per year. We anticipate that we will enroll 67 patients of all genders, races, and ethnicities. Given the hypofractionated course of therapy, 95% of patients should be able to complete therapy. We anticipate that we will accrue approximately 4 patients per month, therefore completing accrual in 15 months. Patients will be accrued from the outpatient clinics and inpatient hospitals of one U.S. site. Potential participants will be identified by our multidisciplinary team physicians and discussed in tumor board.

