### 11.2 Study Endpoints

The co-primary endpoints are rate of local control of the treated (i.e. target) lesion at 6 months, and proportion of patients with treatment related grade 3+ CTCAE v5.0 toxicity. Local control will be determined by RECIST 1.1 analysis of baseline compared with imaging at 6 months. Imaging may include CT scan, PET/CT, or MRI. It is strongly suggested that the same imaging modality is used between baseline and at every follow-up timepoint for staging of disease.

Importantly, there are limited available data to determine expected local control of large tumors after SBRT. Almost all studies have focused on tumors with average maximal diameter of only 5.5 cm corresponding to a tumor volume of approximately 87 cc. In such studies, local control rates are approximately 70-85%. In the pilot study of Lattice SBRT at Washington University, the median treated tumor volume was 435 cc (N=14). Likewise, these few studies of SBRT for large tumors report a grade 3+ toxicity rate of 5-25%, varying based on tumor location.

Due to the lack of a reliable historical comparison, the enrollment target was defined by clinical considerations as opposed to power calculations for comparison with a historical control. This study instead seeks to establish the expected local control rate at 6 months for patients with such large tumors treated with Lattice SBRT. After discussing with internal and external stakeholders, we determined that a clinically reasonable bound on local control at 6 months would be 15%. Approximately 47 patients would be required to determine local control with a 95% confidence interval of +/- 15%; 67 patients will be enrolled to get 47 evaluable patients. We anticipate that up to 30% of patients may not be evaluable for local control at 6 months and are accounting for this potential drop-out rate by enrolling 67 patients. This is because patients with very large tumors needing palliative radiotherapy often have short survival.

Likewise, the study seeks to establish the expected grade 3+ treatment related toxicity rate for treatment of large tumors with lattice SBRT. The treatment will be considered safe if the grade 3+ treatment related toxicity rate is less than 20%, which is in line with prior studies of SBRT of large tumors.

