### **11.5 Accrual**

The rate of accrual for the study is expected to be about 4 patients per month. It is estimated 67 eligible patients will be enrolled in 12 months.

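### Section 11.4 calls all 67 enrolled patients evaluable and says 67 ensures 47, but at the expected 20–30% loss the chance of reaching 47 runs from 0.98 down to 0.55

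*Combined protocol and SAP*

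**What the plan says.** Section 11.4 begins "Approximately 67 evaluable patients will be enrolled". It then sets the precision target: "Approximately 47 patients would be required to determine local control with a 95% confidence interval of +/- 15" percentage points. It describes the expected loss as "we expect 20-30% of patients will complete Lattice SBRT but may be unevaluable for the primary endpoint", and concludes "Enrolling 67 patients with an up to 30% drop out rate would ensure at least 47 evaluable patients".

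Other sections agree on 67 enrolled and 47 evaluable. Section 11.2 says "67 patients will be enrolled to get 47 evaluable patients", with up to 30% not evaluable at 6 months because survival is often short. The Protocol Summary says "67 adult patients will be enrolled and treated, (with a goal of 47 evaluable patients".

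Under Section 5.8 and the Protocol Summary, only participants who receive no treatment are replaced. No replacement is described for a treated patient who dies or has no 6-month imaging.

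On accrual, Section 11.5 gives about 4 patients per month and adds "It is estimated 67 eligible patients will be enrolled in 12 months". Section 4.5 gives the same monthly rate, 50 patients per year and 15 months. The Protocol Summary gives 16 months before treatment and follow-up time.

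**The concern.** There are two faults in one short section. First, the opening sentence attaches the word *evaluable* to the number enrolled, so the section gives two different evaluable counts, 67 and 47. The evaluable count is the denominator of the local-control rate, so it should be stated once and correctly.

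Second, the closing sentence turns an expected count into a guarantee. The enrolment figure is simply the evaluable target divided by the retained fraction at 30% loss. A size set that way meets its target on average, with no margin for chance.

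This matters because Section 11.2 says enrolment was not set by power against a historical control. The ±15-point interval for local control is the one numerical criterion behind the sample size. A reader should be able to see how likely the trial is to meet it, and what the interval becomes if it falls short.

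The accrual duration is a smaller, separate inconsistency next to it.

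**Working it through.** **Inputs.** Target half-width of 15 points at 95% confidence, 47 evaluable, 67 enrolled and 20–30% expected loss (Section 11.4); up to 30% loss and 70–85% local control in earlier SBRT studies of smaller tumours (Section 11.2); replacement of untreated participants only (Section 5.8).

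**1. Reproduce the 47.** For each n, take the largest exact (Clopper-Pearson) 95% half-width over all possible counts. It is 15.1 points at n = 46 and 14.9 at n = 47, so 47 is the smallest n within 15 points. The normal-approximation formula at 50% control, 1.96² × 0.25 / 0.15² = 42.7, gives 43. The plan does not name its method, but the exact interval reproduces its figure.

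**2. Reproduce the 67.** 47 / (1 − 0.30) = 67.1, rounded down to 67. Neither figure is miscalculated.

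**3. The opening sentence.** Taken literally, 67 evaluable at 30% loss would need 67 / 0.70 = 95.7, about 96 enrolled. Every other statement of the size gives 67 enrolled, so the word *evaluable* is the error.

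**4. The assurance.** Let X be the number evaluable out of 67, with patients independent and each lost with probability d. Then X is binomial (67, 1 − d).

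| Loss d | Expected X = 67(1 − d) | P(X ≥ 47) |
|---|---|---|
| 20% | 53.6 | 0.98 |
| 25% | 50.3 | 0.85 |
| 30% | 46.9 | 0.55 |

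At 30% loss the 5th and 95th percentiles of X are 41 and 53.

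**5. What a shortfall costs.** The worst-case exact half-width is 14.9 points with 47 evaluable, 15.4 with 44 and 16.0 with 41. The worst case lies near 50% control. With 41 evaluable, the exact half-width is 14.7 points at 29/41 (71%), 13.0 at 33/41 (80%) and 11.8 at 35/41 (85%). Over the 70–85% range it is therefore about 14.7 points or less.

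**6. Accrual.** 4 per month × 12 months = 48 patients, not 67. At 4 per month, 67 patients take 67 / 4 = 16.75 months. At the 50 per year in Section 4.5 they take 67 / 50 × 12 = 16.1 months. The 15 months in Section 4.5 gives 4 × 15 = 60. The 16 months in the Protocol Summary agrees with 50 per year.

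**The case against.** The best defence is that Sections 11.2 and 11.4 both say *up to* 30%. Read as a ceiling on realised loss, at most 20 of 67 are lost, 47 remain, and the assurance is arithmetically right. This reading is possible. But Section 11.4 introduces the loss as something expected, nothing in the plan enforces a ceiling, and the stated cause, short survival, is outside the sponsor's control.

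The second defence is that the practical effect is small, and this stands. The plan elsewhere says approximately 47 and calls 47 a goal, and a shortfall of a few patients moves the half-width by about a point at worst. The 70–85% control rates come from smaller tumours, and Section 11.2 says there is no reliable historical comparison, so they are not a firm planning value. Still, they are the only control rates in the documents.

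A reader might infer more than the documents support:

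- *That reaching 47 is a coin flip.* The 0.55 belongs to the upper end of a 20–30% range, and at the lower end the probability is 0.98.
- *That non-completion lowers the count further*, since Section 4.5 says "95% of patients should be able to complete therapy" and Section 11.4 describes the loss among patients who complete treatment. Section 11.2 applies the 30% to patients generally, and Section 5.11 keeps those who stop early in scheduled follow-up. Adding 5% to the 30% is not justified.
- *That accrual might close at 12 months with 48 patients.* The target is a number of patients, and no calendar closing rule is stated.
- *That 96 patients were intended.* The Protocol Summary, Section 11.2 and the rest of Section 11.4 rule this out.

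**Conclusion.** The point holds as a fault in what Section 11.4 states, not in the sample size. The first sentence contradicts the rest of the plan on the number evaluable. The assurance of 47 is unsupported when the loss is an expected rate: the probability of at least 47 is 0.98, 0.85 and 0.55 at 20%, 25% and 30% loss. These figures assume independent losses at a constant rate and no replacement of treated patients.

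The consequence for precision is modest. At 30% loss and the 5th percentile of 41 evaluable, the worst-case exact half-width exceeds the target by 1.0 point (16.0 against 15). It stays within the target if local control is 70–85%. The figures 47 and 67 both reproduce and need not change.

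The accrual statement in Section 11.5 is inconsistent with its own rate, and three durations (12, 15 and 16 months) appear in the document. The stated rates support about 16 to 17 months.

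**What to change.** In Section 11.4, replace the first sentence with: *About 67 patients will be enrolled; the goal is 47 evaluable for local control at 6 months.*

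Replace the assurance with: *With 67 enrolled, about 47 to 54 evaluable patients are expected at 30% to 20% loss (probability of at least 47: 0.55 to 0.98). The worst-case exact 95% half-width is 14.9 points with 47 and 16.0 points with 41.* The 54 is 67 × 0.80 = 53.6, rounded.

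Separately, give one accrual duration in the Protocol Summary, Section 4.5 and Section 11.5. On the stated rates it is about 16 to 17 months. Changing Section 11.5 alone would leave the documents inconsistent.

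The cost is wording only. No patients are added and no endpoint or analysis changes; the stated precision simply becomes a little less favourable.
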